16.3.3 Secondary endpoint

To verify whether any relation exists between the accuracy of BrOxy M for both SpO₂ and HR and subject skin pigmentations, and that no adverse events related to the use of BrOxy M will occur, the following routines will be used:

- Sensitive analyses by group of skin pigmentation: above reported analyses can be repeated after stratifying by group.
- ANOVA (analysis of variance): this test allows a comparison of two or more groups.
- Frequency analyses describing whether adverse effects exist.
- Bivariate and multivariate logistic regression analyses evaluating which risk factors may be associated with adverse effects, if these exist.

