7 OBJECTIVES AND ENDPOINTS

7.1 OBJECTIVES

The **primary objective** of the study is to confirm the performance of BrOxy M in comparison with a reference, CE marked, pulse oximeter equipment in a controlled desaturation study.

The **secondary objectives** of the study are:

- To assess BrOxy M performance in subjects with different skin pigmentation (Note: this is a tentative objective, since few subjects are planned to be enrolled and there is no guarantee that they will have different skin pigmentation)
- to confirm BrOxy M safety

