10 STUDY SUBJECTS

The study population will include adult healthy volunteers who will accept to participate in this oxygen desaturation study in a controlled clinical environment. At least 11 healthy subjects will be enrolled. Data collected on the first subject will not be used for accuracy measurements but will serve to finalize the test set up phase and ensure adequate recording procedures are used by site staff. On each of the remaining 10 subjects, 32 paired measurements will be performed in order to obtain a maximum of 320 "valid" measurements (see Section 17.2) which guarantees a statistically significant accuracy study (see point EE2.3.4 of the ISO 80601-2-61: 2017 standard).

To take into account invalid data and potential drop out samples up to 2 additional subjects may need to be enrolled. For this reason sample size for this study will be between a minimum of 11 and a maximum of 13 healthy volunteers.

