16 STATISTICAL ANALYSIS

16.1 OVERVIEW

Statistical analyses will be performed with SPSS, Statistical Package for the Social Sciences (SPSS Inc, Chicago, IL), by following the requirements of the standard ISO 80601-2-61:2017 ("Medical electrical equipment - Part 2-61: particular requirements for basic safety and essential performance of pulse oximeter equipment, Procedure for non-invasive laboratory testing on healthy adult volunteers).

The *significance level*, that is the probability of rejecting the null hypothesis when it is true, will be set to 0.05 (two-sided, corresponding 5% risk of concluding that a difference exists when there is no actual difference).

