16.2 ANALYSIS SETS

Analyses will regard 320 pair measurements (80 in the ambient air, and 80 for each of the four defined target levels, that will be obtained from 10 healthy subjects).

Clinical Investigational Plan			
Protocol No.:	Version 1.0	Dana 25 of 45	
01M2020-CH.LMD	Date: 22 December 2020	Page 35 of 45	

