17.3 DATA PROCESSING

Subject's data from the paper CRF will be entered manually on an electronic clinical database.

Measurements obtained with the reference device and with BrOxy M will be accessed by the Sponsor Data Manager, and processed as follows. After data acquisition from the devices, first 8 valid paired assessments of SpO_2 and HR will be selected from each plateau as follows:

- Reference device: SpO₂ and HR valid values will be selected starting from at least 30" after plateau stabilization, with a time interval between measurements of at least 20".
- BrOxy M: SpO₂ and HR values generated by BrOxy M will be obtained by processing the
 photoplethysmographic signals generated by the device with the BrOxy Medical software. Then,
 SpO₂ and HR values corresponding to the same time points selected for the reference pulse
 oximeter will be chosen.

As a result, it is expected that up to 32 paired (and synchronized) measurements of SpO₂ and HR will be obtained from each enrolled subject, from the reference device and BrOxy M. Once paired measurements for SpO₂ and cardiac frequency have been obtained at the preselected time points (0, 20", 40", etc.) the list of paired observations will be merged with subject's data in the clinical database.

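### The skin-pigmentation ANOVA, read with the stated analysis set, runs on repeated readings with no subject term, so differences between individuals are likely to be taken for pigmentation effects.

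*Combined protocol and SAP*

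**What the plan says.** Section 7.2 makes the relation between skin pigmentation and BrOxy M accuracy a secondary endpoint, for both SpO₂ and HR. For this, section 16.3.3 offers a repeat of the primary routines within pigmentation groups, and "ANOVA (analysis of variance): this test allows a comparison of two or more groups". It does not say which variable enters the ANOVA, how the Fitzpatrick types are grouped, or whether a record is a reading or a person.

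The unit has to be taken from section 16.2: "Analyses will regard 320 pair measurements", "that will be obtained from 10 healthy subjects". Section 10 gives the structure behind that total: "On each of the remaining 10 subjects, 32 paired measurements will be performed". Enrolment may be larger ("sample size for this study will be between a minimum of 11 and a maximum of 13 healthy volunteers"). The first subject is used only for set-up, so 10 to 12 people are analysed. Section 16.1 sets the significance level, which "will be set to 0.05 (two-sided, corresponding 5% risk of concluding that a difference exists when there is no actual difference".

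Section 7.1 calls the pigmentation objective tentative, because few subjects are planned and "there is no guarantee that they will have different skin pigmentation".

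**The concern.** Fitzpatrick type is recorded once per person, at screening. All of a person's readings come from a single test session; within a plateau they are taken "with a time interval between measurements of at least 20" seconds. If BrOxy M reads slightly high or low against the reference on a given person, that offset runs through all of that person's readings.

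An ANOVA on readings with no subject term treats each reading as independent evidence about skin type. With six types in Appendix A and 10 to 12 people, a group may be one or two individuals, counted as 32 or 64 observations. The test then asks whether these particular individuals differ, which is not the endpoint.

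At stake is a claim, on a stated secondary endpoint, that accuracy depends on skin type when only individuals differ. The stratified repeats share the weakness: a group of one person would produce 32-reading results that describe that person alone.

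**Working it through.** **The plan's own figure.** 10 subjects × 4 plateaus × 8 readings = 320, which agrees with section 16.2. (The breakdown there, 80 in ambient air plus 80 at each of four target levels, would literally give 400. The total is right if ambient air is one of the four plateaus, as in Table 1.) The documents give no power, effect size or standard deviation for the pigmentation comparison, so there is nothing further to reproduce.

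**Inputs.** Subjects n = 10 (section 16.2); readings per subject m = 32 (section 10); N = 320; two-sided level 0.05 (section 16.1). Assumed: the ICC, meaning the share of variance in the paired differences that lies between people, from 0 to 0.5; normally distributed subject effects; no true pigmentation effect; all 32 readings available per subject.

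**Information content.** Design effect = 1 + (m − 1) × ICC = 1 + 31 × ICC.

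| ICC | Design effect | Effective readings (320 / design effect) |
|---|---|---|
| 0.01 | 1.31 | 244 |
| 0.05 | 2.55 | 125 |
| 0.1 | 4.10 | 78 |
| 0.3 | 10.30 | 31 |
| 0.5 | 16.50 | 19 |

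**False-positive rate.** With g groups, the reading-level statistic is F = [SS_between / (g − 1)] / [(SS_subject + SS_error) / (N − g)], referred to F(g − 1, N − g). Scale the total variance to 1. With no pigmentation effect, SS_between and SS_subject are λ times chi-square variables on g − 1 and n − g degrees of freedom, where λ = (1 − ICC) + 32 × ICC. SS_error is (1 − ICC) times a chi-square on N − n.

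Hand check, two groups, ICC 0.1:
- λ = 0.9 + 3.2 = 4.1.
- Expected denominator = (8 × 4.1 + 310 × 0.9) / 318 = 311.8 / 318 = 0.98.
- F is therefore inflated about 4.1 / 0.98 = 4.18-fold.
- The critical value is 3.87; √(3.87 / 4.18) = 0.96, and P(|Z| > 0.96) ≈ 0.34.

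From 400,000 draws per setting:

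| ICC | Two groups | Three groups | Four groups |
|---|---|---|---|
| 0 | 5% | 5% | 5% |
| 0.01 | 9% | 10% | 11% |
| 0.05 | 22% | 31% | 39% |
| 0.1 | 34% | 49% | 60% |
| 0.3 | 55% | 77% | 88% |
| 0.5 | 65% | 86% | 94% |

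A raw-data simulation of a 5 v 5 split (4,000 runs) gave 33.2% at ICC 0.1 and 55.0% at ICC 0.3. With equal readings per person, the split does not matter: 5/5, 8/2 and 9/1 agree. Twelve subjects change the two- and three-group rates by no more than 0.005.

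**After correction.** An ANOVA on the 10 subject means gives 5% at every ICC and split tried. Error degrees of freedom fall from 318 to 8 (two groups) or from 317 to 7 (three). At 80% power the detectable difference, in standard deviations of the subject means, is about 2.0 (5 v 5), 2.5 (8 v 2), 3.4 (9 v 1) and 1.8 (6 v 6).

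**The case against.** The strongest objection is that the unit is inferred. The ANOVA bullet would also fit a one-way ANOVA on 10 subject summaries, which would be valid. That stands as a limit on the charge: the analysis is unspecified, and reading level follows only from the general statement in section 16.2. But nothing in section 16 mentions subject means, a random effect or clustering, so an analyst following the text would use the 320 readings.

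Second, the objective is called tentative, and the stratified analyses are permitted rather than required. This lowers the weight of the point. It does not answer it: the caveat warns of too few people or too little variety in skin type, whereas the test as implied errs towards spurious significance. The caveat changes neither the unit nor the test.

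Third, the size depends on an ICC that the documents do not give. That is correct, and at ICC 0.01 the inflation is modest.

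A reader might go further and infer that individual differences will certainly be reported as pigmentation effects. The documents do not support that. A false finding is a probability that depends on the ICC, there is no inflation at ICC 0, and no comparison arises if all volunteers share one type. Nor does this test bear on the primary accuracy comparison.

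**Conclusion.** The point holds as a gap in specification with a likely consequence. Following sections 16.2 and 16.3.3 as written leads to a pigmentation test whose false-positive rate exceeds the 5% in section 16.1 for any ICC above zero. Over ICC 0.05 to 0.5, it is about 22% to 65% with two groups and 31% to 86% with three. These figures rest on the assumed ICC range, normal subject effects and 32 readings per person; the number of groups is also open, because the plan does not define them. As this is a secondary, openly tentative objective, the point should be corrected but does not threaten the primary objective. A valid subject-level comparison at this sample size can detect only very large differences, so the result should be presented as descriptive or exploratory.

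**What to change.** Amend section 16.3.3 as follows:

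- Define the Fitzpatrick groups and the outcome, separately for SpO₂ and HR.
- Replace the reading-level ANOVA with an analysis of one mean difference (and one RMS difference) per subject. A mixed model with a random subject effect is an alternative, provided that pigmentation is tested on degrees of freedom reflecting the number of people.
- Show results by Fitzpatrick type with the number of subjects in each, including any stratified repeats.
- Give estimates with confidence intervals, labelled exploratory.
- State that a group of one person cannot separate the person from the skin type, under any analysis.

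No extra subjects, procedures or data are needed. The cost is much wider intervals and possibly no useful formal test; the precision given up would have come from counting repeated readings as independent people.

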7.2 ENDPOINTS

The **primary endpoint** of the study will be a comparison of the accuracy of SpO_2 and HR measurements obtained with BrOxy M with that obtained with the reference pulse oximeter in paired observations over a range between 80% and 100% SpO_2 .

For each subject, four different saturation plateaus will be set up (i.e. at 97%, 92%, 87% and 82% SpO_2), waiting 30" before starting to keep the SpO_2 level on each plateau for 2.5' in order to obtain 8 measurements in post-processing. These measurements will be at least 20" away from each other, for a total of 32 measurements for each subject, as summarized in Table 1.

The study will follow the procedures described in the standard ISO 80601-2-61:2017 "Medical electrical equipment - Part 2-61: particular requirements for basic safety and essential performance of pulse oximeter equipment".

As **secondary endpoints**, the following will be verified:

• whether any relation exists between the accuracy of BrOxy M for both SpO₂ and HR and subject skin pigmentations as measured with the Fitzpatrick scale.

Clinical Investigational Plan			
Protocol No.:	Version 1.0	Page 22 of 45	
01M2020-CH.LMD	Date: 22 December 2020	1.80 == 0. 10	

• that no adverse events related to the use of BrOxy M, besides a temporary slight skin irritation of the wrist, will occur.

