11.1.2 Eligibility assessment

Subjects will be assessed for eligibility and all inclusion/exclusion criteria will be verified.

Demographic data and medical history of past or present cardiovascular or pulmonary illnesses as well as information on medication currently being taken to address current illnesses will be obtained by the investigator.

Patients will be permitted to receive concomitant therapy as medically required. A record of all concomitant prescription medications will be maintained. Subjects undergoing drug treatments known to interfere with gaseous exchanges or cardiac frequency will be excluded.

A physical examination will be performed which will include the examination of general appearance and body systems as indicated by patient symptoms, with particular attention to the wrist skin. The subject

^{§ 5} minutes after end of test session

^{*} ECG required at screening unless a 12-lead ECG has been performed in the last 2 months prior to screening

^{**}pregnancy test only for pre-menopausal women.

Clinical Investigational Plan			
Protocol No.:	Version 1.0	Page 27 of 45	
01M2020-CH.LMD	Date: 22 December 2020	Page 27 01 43	

will be asked about any known reaction/allergy to any of the device components. Subjects will be assessed for ASA classification and Allen's test.

Systolic/diastolic blood pressure will be recorded after 5 minutes of rest. Wrist circumference will be measured. Skin pigmentation will be measured using the Fitzpatrick scale (see Appendix A).

A 12 lead ECG will be performed (unless the subject had an ECG tracing done in the last 2 months) and blood sample taken to assess hemoglobin parameters (aHb; COHb and MetHb).

For pre-menopausal females a urine or capillary blood pregnancy test will be obtained.

All measurements will be recorded in the CRF.

Once all screening tests/assessments are completed the subject will be determined to be eligible or excluded.

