Appendix A

Fitzpatrick scale

Fitzpatrick Scale

Very Fair always burns cannot tan

Fair sometimes tans

Medium ususally burns sometimes burns usually tans

Olive rarely burns always tans

Brown rarely burns tans easily

Dark Brown never burns always tans

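### No planned analysis uses the order of the Fitzpatrick scale; ANOVA is valid for the pigmentation endpoint but inefficient for a graded effect when three or more types are present

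*Combined protocol and SAP*

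**What the plan says.** Section 7.2 sets the secondary endpoint as "whether any relation exists between the accuracy of BrOxy M for both SpO₂ and HR and subject skin pigmentations as measured with the Fitzpatrick scale". Section 11.1.2 has the scale recorded for every subject at screening. Appendix A lists six categories in order, from "Very Fair always burns cannot tan" to "Dark Brown never burns always tans".

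For the accuracy part of this endpoint, Section 16.3.3 names two routines. One is a between-group test, given as "ANOVA (analysis of variance): this test allows a comparison of two or more groups". The other, listed just before it, repeats the primary analyses within groups: "Sensitive analyses by group of skin pigmentation: above reported analyses can be repeated after stratifying by group". The section does not define the groups, and it does not say whether the unit of the ANOVA is the subject or the paired reading. Two regressions appear nearby, but neither uses skin type as an ordered predictor of accuracy. The linear regression in Section 16.3.2 looks for proportional bias against the average of the two devices. The logistic regression in Section 16.3.3 concerns adverse effects.

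Sections 1 and 7.1 call the pigmentation objective tentative, because the sample is small and a spread of skin types cannot be assured. No power is claimed for it.

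**The concern.** One-way ANOVA gives the same result if the type labels are shuffled. If device error drifts gradually from lighter to darker skin, ANOVA spreads that signal over as many degrees of freedom as there are types minus one. It also spends error degrees of freedom on estimating each type's mean separately. With about 10 subjects there are few to spare. A test along the scale uses one degree of freedom for the effect and leaves eight for error.

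Two things are at stake. A real gradual change is more likely to be missed. The output also contains no single estimate, in SpO₂ points or bpm per Fitzpatrick step, with an interval to show how much or how little the study learned about pigmentation.

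**Working it through.** **The plan's own figure.** Section 10 gives 10 analysed subjects with 32 pairs each, from 4 plateaus of 8 readings: 10 × 4 × 8 = 320, which matches the total in Section 16.2. For pigmentation the number of independent people is 10, or at most 12 if all 13 permitted subjects are enrolled and the first is set aside.

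**Inputs from the documents.** Two-sided level 0.05 (Section 16.1), n = 10 (Section 10), six ordered types (Appendix A).

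**Assumptions, because the documents give no figures.** One mean BrOxy M minus reference difference per subject; between-subject SD of 1 SpO₂ point; a linear change in bias of 0.75 points per step; the mix of types shown in the table.

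**Formulas.** Let x be the type score and SS = Σ(x − mean x)². Under a linear effect both tests have the same noncentrality, λ = (slope/SD)² × SS. The trend test refers to F with (1, n − 2) degrees of freedom. One-way ANOVA on k types refers to F with (k − 1, n − k). Power comes from the noncentral F distribution.

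For types II–V with counts 2/3/3/2, the mean score is 3.5 and SS = 2(2.25) + 3(0.25) + 3(0.25) + 2(2.25) = 10.5. Then λ = 0.5625 × 10.5 = 5.91.

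| Types present (counts) | SS | λ | ANOVA df | Trend power | ANOVA power |
|---|---|---|---|---|---|
| Two adjacent (5/5) | 2.5 | 1.41 | 1, 8 | 18.2% | 18.2% |
| II–IV (3/4/3) | 6 | 3.38 | 2, 7 | 36.7% | 24.6% |
| II–V (2/3/3/2) | 10.5 | 5.91 | 3, 6 | 56.9% | 29.3% |
| I–V (2 each) | 20 | 11.25 | 4, 5 | 83.5% | 38.5% |
| I–VI (1/2/2/2/2/1) | 22.5 | 12.66 | 5, 4 | 87.5% | 30.7% |

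**Other slopes.** At 0.5 per step, the last four rows become 19% against 13%, 30% against 15%, 50% against 19%, and 55% against 16%. At 1.0 per step they become 58% against 41%, 81% against 49%, 97% against 62%, and 98% against 50%. With 12 subjects, types II–V (3 each) and slope 0.75, the figures are 74.5% against 46.1%.

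**Where the ranking changes** (simulation, types II–V, counts 2/3/3/2, SD 1):

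- Only the darkest type shifted by 2 points: trend 26%, ANOVA 32%. Shifted by 3 points: 41% against 63%.
- The upper two types shifted by 2 points: trend 59%, ANOVA 47%.
- No effect: both reject about 5%.

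For a symmetric U-shape over a symmetric mix of types the true slope is zero, so a trend test cannot detect it and ANOVA can.

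**Which accuracy summary.** A mean signed difference does not capture scatter. In a simulation with assumed within-subject SD rising from 1 to 2.5 over types II–V, no change in mean bias, 32 readings per subject and between-subject SD 1, the slope on the mean difference rejected 5% of the time, which is the chance rate. The slope on each subject's RMS difference rejected 85%.

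**The case against.** The strongest reply is that the endpoint asks "whether any relation exists between the accuracy of BrOxy M" and skin type, with no mention of direction or trend. That stands. A reader might infer that the endpoint specifies a change along the scale and that ANOVA is therefore the wrong test. The documents do not support this: ANOVA is a legitimate test of any relation, and it is the better one for some patterns. The defect is inefficiency against a graded effect.

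The size of the loss depends on a mix of types that the protocol does not control. With two types, or subjects collapsed into two groups, the tests are identical. The large gains need types I–V or I–VI among about 10 volunteers at one site, and nothing in the plan secures that. With a narrow spread and a modest slope, neither test has useful power. This stands too.

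The by-group repeats are descriptive, so they should not be counted as a loss of test power.

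The objective is declared tentative and Section 16.3.3 sets no decision rule. A reader might infer that the plan would take a non-significant ANOVA as showing no relation, but it does not say so. The tentative status does not remove the point: in a small exploratory analysis, a slope with its interval shows how much was learned.

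Finally, if the 320 pairs were analysed as independent, false positives would be the larger problem. At an assumed within-subject correlation of 0.1, ANOVA would reject falsely 34% of the time with two types and 77% with six, and a trend test about 34%. The efficiency loss described here therefore applies once there is one value per subject, and the fix must be built on that unit.

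**Conclusion.** The point holds as an improvement to an exploratory analysis. The scale is ordered, and no planned analysis of accuracy uses the order. For a linear effect of 0.75 SD per step and 10 subjects, a test along the scale adds about 12 points of power with types II–IV (36.7 − 24.6), 28 with II–V (56.9 − 29.3), 45 with I–V (83.5 − 38.5) and 57 with I–VI (87.5 − 30.7). It adds nothing with two types, and it can lose if only the darkest type differs or the relation is not monotone.

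These figures rest on an assumed SD, slope and mix of types, and on one value per subject; the documents state none of them. The planned ANOVA is not invalid, and a large loss is not certain. What the plan lacks is a cheap analysis suited to a gradual effect, with an estimate and an interval.

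**What to change.** In Section 16.3.3:

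- For each subject, separately for SpO₂ and HR, compute the mean BrOxy M minus reference difference and the RMS difference.
- Regress each summary on Fitzpatrick type scored 1 to 6, and report the slope per step with its 95% confidence interval. Give Spearman's correlation as a check that does not assume equal steps.
- Plot every subject's value against type.
- Keep the by-group results as description, and ANOVA on one value per subject as a supportive check for non-monotone patterns.
- Label the analysis exploratory, and state that a non-significant result is not evidence of no relation.

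The cost is a few sentences and no new data, since type is already recorded at screening. The small downside is that the trend test is less sensitive if only one extreme type differs; the retained ANOVA, by-group results and plot cover that case.

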5.2 USE OF BROXY M

The BrOxy M device is a wearable medical device with a size similar to that of a watch (see Figure 2) which, thanks to the sensor placed on the side in contact with the skin of the subject's wrist, is able to acquire photoplethysmographic signals and memorize them. With the use of the proprietary software provided by Life Meter S.r.l., it is possible to download the signals stored in the BrOxy M device, view, archive and export them. Such signals can be used as input for algorithms with diagnostic purposes, provided that they are suitably processed with specifically designed software in order to obtain parameters that describe the physiological state of the patient (such as, for example, heart rate or blood oxygen saturation).

According to the product intended use, registration of photoplethysmographic signals using BrOxy M can occur for up to 24 hours. In this study, signal registration will occur for a maximum of around 35 minutes for each enrolled subject. At the end of the signal registration phase, BrOxy M will be placed on the one-station charging base. Recorded signals will be automatically transferred to the PC in use for the study and archived in an electronic medical record set up for each enrolled subject. The signals recorded with the device will then be processed by a Sponsor delegate with the software for medical use provided by Life Meter S.r.l.

Detailed procedures covering installation of the one-station recharge base, software installation on the PC, use of BrOxy M bracelet, use of proprietary software and other details are fully described in the BrOxy M User Manual.

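### Eleven to thirteen short sessions cannot confirm device safety, and the planned logistic regression is too imprecise to identify risk factors

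*Combined protocol and SAP*

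**What the plan says.** The Synopsis and Section 7.1 list as a secondary objective "to confirm BrOxy M safety". Section 7.2 makes this an endpoint: it will be verified that no adverse event related to the device, "besides a temporary slight skin irritation of the wrist, will occur". Section 16.3.3 repeats the endpoint without the exception for wrist irritation. It then plans frequency analyses of adverse effects, followed by "Bivariate and multivariate logistic regression analyses evaluating which risk factors may be associated with adverse effects, if these exist". It names no risk factors, minimum number of events, sparse-data method or confidence interval.

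On size, Section 10 states that "sample size for this study will be between a minimum of 11 and a maximum of 13 healthy volunteers". The first subject is for set-up: "Data collected on the first subject will not be used for accuracy measurements but will serve to finalize the test set up phase". The upper end of the range is an allowance: "To take into account invalid data and potential drop out samples up to 2 additional subjects may need to be enrolled". Section 16.2 defines the only analysis set: "Analyses will regard 320 pair measurements", taken from 10 subjects. There is no safety set.

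On exposure, Section 5.2 states that "signal registration will occur for a maximum of around 35 minutes" per subject. Section 10.6 puts the whole session, with preparation and final checks, at about 50 minutes. Section 5.3 gives 24 hours as typical contact with the wrist. Under Section 11.2 a subject with no abnormality leaves the study after a blood pressure check 5 minutes after the test.

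**The concern.** An objective to confirm safety, checked only by the absence of events, needs enough subjects and exposure for that absence to be informative. Here the numbers are small and the wear is brief. The endpoint also sets aside the one effect of BrOxy M itself that Section 15.2 anticipates. A clean result is therefore likely even if related events are not rare, and nothing in the plan requires the report to show which rates remain possible.

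The regression raises the opposite risk. If a few events occur, a model with several covariates could produce infinite or wildly uncertain odds ratios that are then read as risk factors. At stake is a post-market report that states confirmed safety, or names risk factors, on data that support neither.

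**Working it through.** **The plan's own figures.** 1 set-up subject + 10 = 11; 11 + 2 = 13; 10 subjects × 32 pairs = 320. These reproduce, but they count measurements for accuracy. No expected event rate, margin, power or precision is given for safety, so there is no safety figure to reproduce.

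**Zero events.** For n subjects with no event, the exact (Clopper-Pearson) two-sided 95% upper limit is 1 − 0.025^(1/n), and the one-sided 95% limit is 1 − 0.05^(1/n). With true subject-level rate p, the chance of seeing no event is (1 − p)^n. The values of p are assumptions.

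| n | two-sided limit | one-sided limit | no event, p = 5% | no event, p = 10% | no event, p = 20% |
|---|---|---|---|---|---|
| 10 | 30.8% | 25.9% | 60% | 35% | 11% |
| 11 | 28.5% | 23.8% | 57% | 31% | 9% |
| 13 | 24.7% | 20.6% | 51% | 25% | 6% |

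The n = 10 row applies if safety follows the only set in Section 16.2. For scale, a one-sided limit of 10% needs 29 subjects without an event, and a limit of 5% needs 59. These thresholds are illustrative; the plan sets none.

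**Exposure.** 35 min / 1,440 min = 2.4% of a 24-hour wear; 50 / 1,440 = 3.5%. Total recording is at most 11 × 35/60 = 6.4 to 13 × 35/60 = 7.6 subject-hours. Taking the full session as an upper limit for contact gives 11 × 50/60 = 9.2 to 13 × 50/60 = 10.8 subject-hours, or 38% to 45% of one 24-hour wear.

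**Can the logistic model be fitted?** With 0 events it cannot. For 1 to 6 subjects with events, 1,500 data sets per setting were simulated with covariates unrelated to outcome, and each was checked for complete or quasi-complete separation (no finite estimate). The covariates are assumptions, because the plan names none. Ranges cover n = 11 and n = 13.

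- 1 event: separated in 100% of data sets with any binary covariate; 73% to 77% with three continuous covariates; 15% to 18% with one.
- 2 events: 79% to 80% with two binary and one continuous covariate; 49% to 50% with one binary; 13% to 15% with two continuous.
- 3 events: 50% to 56% with two binary and one continuous covariate.
- 5 or 6 events, two covariates: 1% to 10%.

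At an assumed rate of 5%, the chance of at least 2 subjects with an event at n = 13 is 13.5%; at 10% it is 37.9%.

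**Is a fitted model informative?** Take the most favourable case at n = 13: one binary covariate and cells of 3, 3, 3 and 4. SE(log OR) = √(1/3 + 1/3 + 1/3 + 1/4) = √1.25 = 1.118. The 95% interval factor is exp(1.96 × 1.118) = 8.9, so the interval runs from OR/8.9 to OR × 8.9. The true odds ratio needed for 80% power is exp((1.96 + 0.84) × 1.118), about 23. Any other cell split or further covariate widens this. With two covariates, at most 6 subjects in the smaller outcome group leaves 6/2 = 3 per covariate.

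**The case against.** Several points on the other side stand.

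- The regression is conditional on events existing, so the zero-event case is covered, and no decision depends on it.
- A reader might infer that a multivariate model cannot be estimated at all in 11 to 13 subjects, or that there will be fewer than one event per covariate. The documents do not support this. They name no covariates and give no event rate. The regression bullet speaks of adverse effects without limiting them to the device. Section 15.1 counts procedure-related events, and Section 15.2 anticipates rises in heart rate and blood pressure and mild hyperventilation. If these were counted and occurred in 5 or 6 subjects, a two-covariate model would usually converge.
- The frequency analysis is feasible at any sample size, and Sections 11.3 and 15.3 already require every adverse event to be recorded. It would be wrong to say that the whole safety analysis is unworkable.
- A reader might take 35 minutes as skin contact and conclude that total wear is under a third of one 24-hour use. The 35 minutes limits recording; contact can run longer within the session of about 50 minutes.
- The plan nowhere claims to show safety over 24 hours, the device is already CE marked, and safety is a secondary objective.

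These points narrow the concern but do not remove it. Convergence does not give useful precision, and event recording does not supply an interval. The objective remains unqualified, while the skin-pigmentation objective beside it in Section 7.1 is called tentative because few subjects will be enrolled.

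**Conclusion.** The concern holds in this form: absence of related events cannot confirm safety here, and the logistic regression cannot usefully identify risk factors. A clean result leaves a subject-level rate of up to 28.5% (n = 11) or 24.7% (n = 13) compatible with the data, or 30.8% if 10 subjects count, and it speaks only to a single session lasting about 3.5% of a typical wear. The limits need no assumption beyond independent subjects with a common event rate. The probabilities of a clean result rest on the assumed rates of 5% to 20%.

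The regression is inestimable at 0 events. At 1 or 2 events it is often separated, above all with binary or several covariates. At higher counts it may converge but stays too imprecise, with an interval factor of at least 8.9 at n = 13. The separation frequencies rest on assumed covariates; the interval factor is a large-sample approximation for the best case. This should be changed, but it does not affect the primary accuracy endpoint.

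**What to change.** 1. In Section 16.3.3, delete the bivariate and multivariate logistic regressions. Keep the frequency analysis and add a listing of every event by relatedness and severity.
2. Report the proportion of subjects with a device-related adverse event with an exact (Clopper-Pearson) 95% confidence interval, once including and once excluding temporary slight wrist irritation. Show procedure-related events separately. Use one term throughout, since Section 16.3.3 moves between device-related adverse events and adverse effects and omits the exception in Section 7.2.
3. In Section 16.2, define a safety set of all subjects on whom BrOxy M was placed, including the first (set-up) subject, separate from the 10-subject accuracy set.
4. In the Synopsis and Section 7.1, reword the objective along these lines: *describe adverse events during a single short test session (about 35 minutes of recording, session about 50 minutes)*. Do not state in the report that safety is confirmed.

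The cost is a change of wording and a less favourable safety statement. No new data, visits or subjects are needed.
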